3.5 Administration

Studies 1A and 1B

Participants allocated to PlayMed and to the OP will be given the appropriate access for 8 weeks (instructions provided in the study envelope). Participants allocated to the control guidelines will receive a print-out of the guidelines. Participants will be encouraged to engage with their additional educational tool as often as they wish during their eight weeks. In the 8th last week participants will have their knowledge and clinical performance assessed as outlined below.

Studies 2A and 2B

Participants allocated to PlayMed, OP and control guidelines will be given 5 days to utilise their assigned teaching tool. Five days was selected as an appropriate time-frame in which participants would be able complete all cases of the game or online package, or read through the guidelines with minimal impact on their personal and academic schedules. Participants will receive an email with access to their intervention from an unblinded administrator. Participants will have their knowledge and clinical performance assessed as outlined below.

3.6 Assessment & Outcomes Measures

Studies 1A and 2A

Participants will be assessed for:

1. Primary outcomes

- Knowledge acquisition
 - Participant knowledge will be assessed using a 10-point single-best option multiple-choice questionnaire (MCQ); correct answers, with an explanation, will be provided to all participants at the end of the study via email.
- Clinical performance
 - Participant clinical skills will be assessed via an observed structured clinical examination (OSCE) administered in the simulation laboratory (immediately after the knowledge test); participants will be tested across two clinical scenarios. Strict marking criteria will be used to ensure standardisation, with a total possible maximum score of 30. Individual feedback will be provided by assessors immediately after each scenario.

2. Secondary outcomes

- Educational experience
 - Participants will be asked to complete a short survey using 5-point Likert scale (strongly agree, agree, neutral, disagree, strongly disagree). Students will be asked for comments (free text responses) regarding their engagement with, and perception of the educational value, of the learning tool.

The time commitment required of participants for assessment will be approximately 60 mins.

Studies 1B and 2B

Participants will be assessed for:

1. Primary outcomes

- Knowledge acquisition
 - Participant knowledge will be assessed using a 15-point single-best option MCQ; correct answers, with an explanation, will be provided to all participants at the end of the study via email.
- Clinical performance
 - Participant clinical skills will be assessed via an OSCE administered in the simulation laboratory (immediately after the knowledge test); participants will be tested across two clinical scenarios. Strict marking criteria will be used to ensure standardisation, with a total possible maximum score of 50. Individual feedback will be provided by assessors at the conclusion of the OSCE portion of the assessment.

2. Secondary outcomes

- Educational experience
 - Participants will be asked to complete a short survey using 5-point Likert scale (strongly agree, agree, neutral, disagree, strongly disagree). Students

will be asked for comments (free text responses) regarding their engagement with, and perception of the educational value, of the learning tool.

- Future impact on clinical practice
 - Participants will also complete a short post-assessment survey 3 months after their formative assessment date. The short survey contains 7 questions and should take 5 minutes to complete. This survey is powered by Qualtrics (<https://www.qualtrics.com/au/>).

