2.1 Lay Summary & Aims

Medicine has traditionally been learned through the face-to-face lecture, clinical experience on hospital wards, and student self-direction to additional resources such as textbooks and clinical guidelines. Recently educators have sought to improve student learning by providing adjuncts to these methods. The rapid development of computerized technology has seen the emergence of online educational packages in medical programs throughout the world.

‘PlayMed’ is a serious computer game that has been developed to teach paediatrics to medical students. It allows students to learn and apply clinical algorithms for managing patients in a safe, simulated environment. Preliminary data gained from a pilot study suggests that PlayMed improved students’ knowledge of asthma management. However, the efficacy of PlayMed as a learning tool has not been tested against alternative online educational tools, therefore we propose to conduct a randomized control trial of PlayMed using an online educational package as a control. Furthermore, we aim to assess the utility of PlayMed in different populations including nurses and doctors.

We have targeted two common and important paediatric clinical presentations (asthma and seizures) as the focus of our teaching and assessment in this study. It is likely that students will be exposed to both of these conditions during their clinical attachments; the acute management of both conditions is outlined in current NSW Health Paediatric Clinical Practice Guidelines (CPG); and both asthma and seizure disorders are listed in the Australian Curriculum Framework For Junior Doctors. The current UNSW Phase 3 Children’s Health course includes one lecture on each clinical problem.

Under the “G4MER” Program, we plan to perform a series of randomised control trials to see if PlayMed is an effective teaching adjunct to our standard course(s), and if this game is more effective than other online packages for medical students, doctors and nurses. We hypothesise that participants exposed to the game (in addition to standard teaching) will demonstrate superior knowledge and clinical skills compared to those exposed to the alternative online packages, and to those who only receive standard teaching. Additionally, we hypothesise that increased time spent playing the game will improve performance in knowledge-based and clinical assessments.

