2.2 Background Literature Review

The efficacy of both online learning and simulation-based teaching have been well established in Medical Education.^{1,2} Online learning is most effective when students are required to interact either with the package or with each other, and feedback is provided.¹ Simulation is effective as it allows learners to engage in repetitive practice, in a safe environment, with a degree of clinical variation and a range of levels of difficulty. Timely feedback is also vital to effective learning.³

Computer-based simulation games can be defined as instruction delivered via personal computer that immerses trainees in a decision-making exercise in an artificial environment in order to learn the consequences of their decisions.⁴ Computer-based simulation games combine the most effective elements of both online learning and simulation - the online environment provides an easily accessible, interactive yet safe space for students; feedback is provided to the student, and clinical variation with a range of levels of difficulty can be provided.

Little empirical evidence on the effectiveness of educational video games on students' educational outcomes is available. A recent innovative study at UNSW by Dobrescu et al⁵ compared the effectiveness of teaching introductory economics via a video game or traditional textbook learning. This study suggested that there was no difference in exam performance for either modality; however, the video game was considerably more enjoyable as a learning tool. To our knowledge there are no educational role-playing games available on the market which targets the education of medical or nursing students. Currently online learning packages for paediatric clinical practice guidelines are available through HETI Online (<https://hetionline.cit.health.nsw.gov.au/>). At present these are not part of mandatory training.

The development of an online game is an expensive and resource intensive process but may well be an effective adjunct to current teaching programs. We wish to test this product to see if further investment is worthwhile.

3. Study Protocol

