3.1 Research Design Outline

The “G4MER” Program aims to perform a series of randomised control trials on different groups at Sydney Children’s Hospital Randwick:

- (1) **Study 1A** (Formerly titled “Serious Games in Medical Education – a Randomised Control Trial”) involves Phase 3 medical students at UNSW having 8 weeks access to the game, an Online Package (OP) or NSW State Guidelines on Asthma and Seizure management (control). Students are then assessed using multiple choice questions (MCQ) and two observed structure clinical examination (OSCE) stations (detailed below).
- (2) **Study 1B** is also a randomised control trial similar in design to Study 1A, however it will involve doctors and nurses employed at Sydney Children’s Hospital. PlayMed will be compared against the HETI Learning Path Paediatric Clinical Practice Guidelines (Online Package for staff).
- (3) **Study 2A** is identical to Study 1A except participants will have 5 days access to their educational tool. Participants will then undergo the same assessment using multiple choice questions (MCQ) and two observed structure clinical examination (OSCE) stations.
- (4) **Study 2B** is identical to Study 1B except participants will have 5 days access to their educational tool. Participants will then undergo the same assessment using multiple choice questions (MCQ) and two observed structure clinical examination (OSCE) stations.

The proposed study designs are all investigator blinded randomised control trials. Participants may only be involved in Study 1 or Study 2, not both.

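### Studies 1A and 2A: assessor feedback falls between the two OSCE scenarios of a primary outcome, a low-severity point that the 1B/2B timing would avoid

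*Combined protocol and SAP*

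**What the plan says.** Section 3.6 lists clinical performance, measured by OSCE, as a primary outcome for Studies 1A and 2A, and section 4.1 includes OSCE scores in the primary analyses. Each participant takes two scenarios, marked "with a total possible maximum score of 30". No split of marks by scenario is given. On feedback, the section says: "Individual feedback will be provided by assessors immediately after each scenario". It adds: "The time commitment required of participants for assessment will be approximately 60 mins".

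For Studies 1B and 2B the same section says instead: "Individual feedback will be provided by assessors at the conclusion of the OSCE portion of the assessment". Section 3.1 says that Study 1B "is also a randomised control trial similar in design to Study 1A". No reason is given for the different timing.

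The protocol regards feedback as a means of learning. Section 2.2 states: "Timely feedback is also vital to effective learning". Section 5.1 counts OSCE feedback among the learning opportunities that participants gain.

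**The concern.** The OSCE in Studies 1A and 2A is there to test whether participants given the game "will demonstrate superior knowledge and clinical skills compared to those exposed to the alternative online packages", and those given standard teaching only. For that purpose it should record what participants can do after their allocated tool. With feedback after each scenario, that holds for scenario 1 only. Scenario 2 records what they can do after the tool plus individual coaching from an assessor, and the two are added into one score.

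The coaching is individual, so participants who did worse on scenario 1 may have more to gain from it. If they are more common in one arm, the arms would move closer together on scenario 2, and the total would show a smaller difference than the tools alone produced. At stake is the sensitivity of one of the two primary outcomes, in two of the four studies.

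**Working it through.** The point rests on sequence, so most of the check is to set the provisions side by side.

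**1. Order of events.**

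| | Studies 1A and 2A | Studies 1B and 2B |
|---|---|---|
| First | MCQ | MCQ |
| Second | Scenario 1 | Scenario 1 |
| Third | Feedback on scenario 1 | Scenario 2 |
| Fourth | Scenario 2 | Feedback on the OSCE |
| Fifth | Feedback on scenario 2 | none |
| OSCE maximum | 30 | 50 |

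Only the left column has a learning input before a scored scenario. The MCQ is unaffected in all four studies: it precedes the OSCE, and its answers are withheld until the end of the study.

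**2. Does anything else in the plan remove the problem?** No. The plan does not fix or balance the order of scenarios, plans no analysis by scenario, and does not say whether one assessor sees both.

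**3. What the feedback can do to the comparison.** For PlayMed against either comparator, let D1 be the difference in mean marks on scenario 1, D2 the difference on scenario 2 had no feedback come before it, and c the mean gain on scenario 2 from feedback in the PlayMed arm minus that gain in the comparator arm.

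- With the 1B/2B timing, the difference in totals is D1 + D2.
- With the 1A/2A timing, it is D1 + D2 + c.

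Take D1 and D2 as favouring PlayMed, as the plan hypothesises:

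- Equal gains in both arms: c = 0, and nothing changes.
- Larger gain in the weaker arm: c < 0, and the difference is diluted.
- Larger gain in the stronger arm: c > 0, and the difference widens.
- Feedback on scenario 1 covers nothing that scenario 2 tests: both gains are zero, and c = 0.

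**4. Type I error.** If the tools have the same effect, the arms reach scenario 1 alike, receive the same kind of feedback, and reach scenario 2 alike. Then D1 = D2 = c = 0, and no false difference arises from the timing. This assumes that assessors do not know the allocation. Section 3.1 describes all the designs as investigator blinded, and section 3.4 keeps the allocation record with the student co-ordinators.

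**5. Can c be given a number?** No. The plan states no OSCE effect, OSCE standard deviation, marks per scenario or mark-sheet items. Section 3.7 gives a pilot effect for the quiz only (7.0 against 6.0, SD 1.4), which says nothing about how feedback carries from one clinical scenario to another. The plan has no figure of its own on this point to reproduce.

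**The case against.** The strongest reply is that the randomised comparison stays fair. All arms get the same feedback from assessors who are meant to be blinded. That stands. A reader might infer that the timing biases the trial towards one arm or makes the OSCE result invalid; step 4 of the working shows why the documents do not support that.

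Second, carry-over may be slight. The study names "two common and important paediatric clinical presentations (asthma and seizures) as the focus of our teaching and assessment in this study", so one scenario on each condition is the natural reading, though it is not stated outright. Feedback on one would then help the other mainly through general skills. If weaker performers gain more, the spread of scores within each arm may also shrink, leaving the standardised difference little changed. Both arguments stand. A reader might be tempted to quote a loss of power; any such figure would come from assumptions, not from the plan.

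Third, the different timing in 1B and 2B is not a contradiction, though it could be read as one. Similar does not mean identical: the studies also differ in population, MCQ length (10 against 15) and OSCE maximum (30 against 50). Section 3.3 offers students a formative assessment with feedback, and prompt feedback suits that aim. The documents do not say that this is why the timing differs. What the contrast does show is that the plan already uses an alternative for a similar assessment.

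Nor does section 5.1 need to be read as conflicting with section 3.6. Its remarks on OSCE feedback are general, and its phrase about feedback following the OSCE already fits the later timing.

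**Conclusion.** The point holds as a low-severity improvement. In Studies 1A and 2A, scenario 2 contributes to a primary score after a learning input outside every allocated tool, and the plan neither explains this nor allows for it. That follows from the text alone.

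The effect on the between-group OSCE difference is uncertain in size and direction. Dilution is the most plausible direction, on the assumption that weaker performers gain more from individual feedback. Widening is possible but less plausible. The effect could be near nil if the two scenarios share few skills. Given blinded assessors, the timing does not by itself inflate type I error. The MCQ, and the whole of Studies 1B and 2B, are untouched.

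**What to change.** **If assessments in the study concerned have not started:** in section 3.6, under Studies 1A and 2A, replace the feedback sentence with the one already used for 1B and 2B, "Individual feedback will be provided by assessors at the conclusion of the OSCE portion of the assessment", and add the clause: after both scenarios have been scored.

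This costs one sentence. Feedback on scenario 1 becomes slightly less immediate, within a session of about 60 minutes. The feedback promised at recruitment is still given. Because the plan does not say whether one assessor sees both scenarios, notes on scenario 1 may have to be kept or handed over. The 1B/2B text mentions no extra staff or procedure.

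**If assessments in a study have already begun:** do not change the timing midway, since one primary score would then mix two measurement conditions. Keep the total as the primary score and report the feedback between scenarios as a limitation.

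The documents do not state how far either study has progressed, so the choice is made separately for 1A and 2A. If only one is changed, section 3.6 must give the timing for each, and the statement in section 3.1 that 2A uses the same assessment needs a qualifying phrase. Section 4.1 plans no comparison between the two studies, so the planned analyses are unaffected.

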3.7 Sample Size

Study 1A

GLIMMPSE (<http://glimmpse.samplesizeshop.org/#/>) was utilised for sample size calculation with equal group sizes (i.e ratio of groups 1:1:1). In our initial pilot study, the mean quiz scores were 7.0 (SD 1.4) and 6.0 (SD 1.4) for the PlayMed and control cohorts (standard teaching only) respectively.⁶ If we assume that students in the OP cohort will achieve quiz scores of 50% the difference between PlayMed and controls (i.e. score of 6.5), then the following sample size is required:

- A total of 54 subjects (i.e. 18 in each group) to be able to reject the null hypothesis that the population means of the experimental and control groups are equal with probability (power) 0.8. The Type I error probability associated with this test of this null hypothesis is 0.05.
- Assuming a total drop-out rate of 20%, we will recruit 22 subjects for each group, i.e. 18 PlayMed, 18 OP and 18 controls.

Study 2A

Given we have no preliminary data for doctors and nurses, the same sample size estimate will be used for this study. We will recruit 22 subjects for each group, i.e. 22 PlayMed, 22 OP and 22 controls.

Studies 1B and 2B

The same sample size estimates will be utilised for these studies. For each study we will recruit 22 subjects for each group, i.e. 22 PlayMed, 22 OP and 22 controls.

4. Statistical Analysis Plan (SAP)

All Studies

Descriptive and inferential statistics will be used. Normally distributed data will be presented by mean and standard deviation (SD) and non-normally distributed data will be presented by median and interquartile range (IQR). Binary and categorical data will be presented using counts and percentages. R v3.4.4 will be used for all statistical analyses.

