4.1 Primary Outcomes

All Studies

The primary analyses will compare: (1) PlayMed vs OP; and (2) PlayMed vs control guidelines on their mean/median: (i) MCQ score, and (ii) OSCE scores. Comparisons will be made using an unpaired t-test or a Mann-Whitney test for parametric and non-parametric data, respectively. P-values <0.05 will be considered statistically significant.

Effect sizes for will be calculated using Cohen's d (d) with 95% confidence intervals (95%CI) using the 'effsize' package.⁷ Effect sizes will be considered small if $0.2 \leq d < 0.5$, medium if $0.5 \leq d < 0.8$, and large if $d \geq 0.8$.

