4.3 Missing Data

The primary analyses will be performed using a modified intention-to-treat (ITT) basis. For participants who are randomised and do not attend for assessment, a mean imputation of the assessment scores from their allocation group will used. A sensitivity, per-protocol analysis will also be performed, with no restrictions placed on the minimum time spent using the allocated intervention.

5. Informed Consent Forms (ICF)

Studies 1A and 2A

Written consent will be gained from the Medical students using the consent forms attached to the application.

Studies 1B and 2B

Written consent will be gained from the medical and nursing staff using the consent forms attached to the application.

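### Section 3.7 claims 80% power with 18 per group, but its own means and SD give about 55% for PlayMed vs control (68% one-sided) and 18% for PlayMed vs OP

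*Combined protocol and SAP*

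**What the plan says.** Section 3.7 (Sample Size) takes its inputs from a pilot in which "the mean quiz scores were 7.0 (SD 1.4) and 6.0 (SD 1.4) for the PlayMed and control cohorts". It assumes that the OP group will fall halfway between, at 6.5. From a GLIMMPSE calculation with equal groups it concludes: "A total of 54 subjects (i.e. 18 in each group) to be able to reject the null hypothesis", with power 0.8 and Type I error 0.05. The hypothesis that GLIMMPSE tested, the test used and its sidedness are not reported.

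The section allows for 20% drop-out, and the recruitment line then gives two sizes: "we will recruit 22 subjects for each group, i.e. 18 PlayMed, 18 OP and 18 controls".

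For Study 2A the same number is reused with the reason "Given we have no preliminary data for doctors and nurses", although 2A enrols medical students. For 1B and 2B: "The same sample size estimates will be utilised for these studies". Section 3.6 gives the staff studies a different instrument: "Participant knowledge will be assessed using a 15-point single-best option MCQ".

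Section 4.1 sets the analysis: "The primary analyses will compare: (1) PlayMed vs OP; and (2) PlayMed vs control guidelines", each on MCQ and OSCE scores, by unpaired t-test or Mann-Whitney test at P < 0.05. Section 4.3 says that for randomised participants who do not attend assessment "a mean imputation of the assessment scores from their allocation group will used".

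**The concern.** A 1.0-point difference with SD 1.4 is a standardised difference of about 0.71. Eighteen per group is too few to detect that with 80% power in an ordinary two-sample comparison, so the claim had to be checked against its own inputs.

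This is the only power statement in the plan, and it supports all four studies. Section 2.2 says the trial is meant to inform whether further investment in the game is worthwhile. A reader who trusts 80% power would take a non-significant MCQ result as coming from an adequately sized trial. The risk is greatest for PlayMed vs OP, where the assumed difference is half as large and no power is stated.

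**Working it through.** **Inputs** (section 3.7): means 7.0, 6.5, 6.0; SD σ = 1.4; α = 0.05; n = 18 per group; stated power 0.80. The test (section 4.1) is a pairwise unpaired t-test. Sidedness is not stated, so both versions are shown.

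**1. PlayMed vs control by t-test.** d = 1.0/1.4 = 0.714. The noncentrality is d√(n/2) = 0.714 × √9 = 2.143 on 2n − 2 = 34 df.
- Two-sided, critical value 2.032: power **0.549**.
- One-sided, critical value 1.691: power **0.675**.

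**2. Three-group F test.** The squared deviations from the mean of 6.5 sum to 0.25 + 0 + 0.25 = 0.5. So λ = 18 × 0.5/1.96 = 4.59 on 2 and 51 df, with critical value 3.18: power **0.445**.

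**3. PlayMed vs OP by t-test.** d = 0.5/1.4 = 0.357, noncentrality 1.071: power **0.180** two-sided and 0.276 one-sided.

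**4. Effect of the number assessed, and the size needed for 80%.**

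| Test | n = 18 | n = 22 | n per group for 80% |
|---|---|---|---|
| PlayMed vs control, two-sided t | 0.549 | 0.639 | 32 |
| PlayMed vs control, one-sided t | 0.675 | 0.754 | 25 |
| Three-group F | 0.445 | 0.533 | 39 |
| PlayMed vs OP, two-sided t | 0.180 | 0.212 | 125 |

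The expected number assessed is 22 × 0.8 = 17.6 per group. At 17, two-sided power for PlayMed vs control is 0.524.

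**5. Can 0.80 be recovered?** With n = 18, SD would have to be about 1.04 (two-sided t) or 0.94 (F). Pooling both active arms against control (0.75 points, 36 vs 18) gives 0.445 two-sided and 0.574 one-sided. Putting all 54 into two groups of 27 gives 0.731 two-sided and 0.828 one-sided, but the text specifies 18 in each of three groups. Reading 1.4 as a variance and also testing one-sided gives 0.799, but the text says SD. The GLIMMPSE settings are not printed, so the cause cannot be determined.

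**6. Does the mean imputation in section 4.3 make up the shortfall?** Take m = 18 observed and 4 imputed at the group mean, so N = 22. Group means do not change, but the pooled variance is divided by 2N − 2 = 42 instead of 34 and the standard error uses 22 instead of 18. The t statistic is therefore inflated by √[(22/18) × (42/34)] = 1.229. The nominal critical value of 2.018 becomes 2.018/1.229 = 1.642 on a valid 34-df scale. The rejection rate is then 0.693 for a 1.0-point difference, 0.296 for 0.5 points and **0.110 when there is no difference**. With 17 observed and 5 imputed the rates are 0.704, 0.319 and 0.131. Simulation of 400,000 trials agreed. This is not power at α = 0.05, and it is still below 0.80.

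**7. Detectable difference.** Solving the two-sided t-test for 80% power gives d = 0.961 at n = 18, which is 0.961 × 1.4 = 1.35 points. At n = 17 it is d = 0.991, or 1.39 points.

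**8. Recruitment line.** 18/(1 − 0.2) = 22.5, which rounds up to 23. The plan says 22 and then lists 18/18/18.

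**The case against.** Several points can be made for the plan.

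- *Sidedness.* Section 2.1 states a directional hypothesis and neither 3.7 nor 4.1 says two-sided. Read one-sided, the shortfall is about 12 percentage points (0.68 against 0.80), not 25. That is a fair qualification of the size. Two-sided remains the ordinary reading of a P < 0.05 rule, and the one-sided figure also misses 0.80.
- *Rounding and hidden settings.* The pilot values are given to one decimal and the GLIMMPSE inputs are not shown. At the most favourable rounding (difference 1.1, SD 1.35), power at 18 per group is 0.77 one-sided and 0.66 two-sided, still short.
- *Which comparison is meant.* The null hypothesis refers only to experimental and control groups. It could mean PlayMed vs control, an overall test, or both active arms against control. None of these reaches 0.80.
- *Precision will be visible.* Section 4.1 promises Cohen's d with 95% confidence intervals, which would show how imprecise a null result is. That helps, but only partly: intervals computed on mean-imputed data would be too narrow.
- *Separate matters.* The missing power for PlayMed vs OP and for the OSCE are omissions, not arithmetic errors, and the lack of preliminary staff data is disclosed. That is correct. They show how far the single figure is being stretched, but the finding does not depend on them.

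**Conclusion.** The concern holds. On the printed inputs, 18 per group gives 55% power for PlayMed vs control with a two-sided t-test, about 25 percentage points below the stated 80%. One-sided it is 68%, about 12 points below, and for a three-group F test it is 45%. No reading consistent with three groups of 18 and SD 1.4 reaches 0.80, nor does assessing all 22 per group. For PlayMed vs OP, the assumed 0.5-point difference would be missed about four times in five.

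These figures assume normally distributed scores, a common SD of 1.4 and the means in section 3.7. The imputation figures also assume equal, random drop-out, but the main result does not use them. For the staff studies no power on the point scale can be given, because the 15-point MCQ has no pilot SD.

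**What to change.** Keep the recruitment target, remove the 0.8 claim from section 3.7 and replace it as follows.

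- **Study 1A, and 2A by assumption (same 10-point MCQ):** *For the MCQ score, with about 18 participants per group actually assessed (no imputed scores), two-sided alpha 0.05 and SD 1.4, power is about 55% for PlayMed vs control (1.0 point) and 18% for PlayMed vs OP (0.5 point); the difference detectable with 80% power is about 1.35 points.*
- **Studies 1B and 2B:** do not carry over the 0.8 claim or any figure in points. State only: *About 18 participants assessed per group gives 80% power for a standardised difference of about d = 0.96.*
- **OSCE:** say that no power calculation was made.
- **Interpretation:** add that a non-significant PlayMed vs OP result will not be read as showing no difference.
- **Clerical:** reconcile the recruitment line to 22 randomised per group, with 17 to 18 expected to be assessed after 20% drop-out.

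The cost is wording only. The stated power becomes less favourable, and the sample size then rests on the detectable difference instead of an 80% target. Sample size, outcomes and tests do not change, and no extra participants are needed.

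### The Study 1A recruitment sentence gives two targets, 22 per group and then 18; separately, and as a minor point, 22 falls just short of covering the stated 20% drop-out

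*Combined protocol and SAP*

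**What the plan says.** Section 3.7 (Sample Size) first gives the requirement for Study 1A: "A total of 54 subjects (i.e. 18 in each group", for a power of 0.8 with a Type I error of 0.05. The inputs are pilot results, "the mean quiz scores were 7.0 (SD 1.4) and 6.0 (SD 1.4) for the PlayMed and control cohorts", and an assumed online-package mean halfway between them (6.5).

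The next bullet turns this into a recruitment target: "Assuming a total drop-out rate of 20%, we will recruit 22 subjects for each group, i.e. 18 PlayMed, 18 OP and 18 controls".

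Study 2A takes over the same estimate: "We will recruit 22 subjects for each group, i.e. 22 PlayMed, 22 OP and 22 controls". The line for Studies 1B and 2B also gives 22 in each of the three groups. No formula for the drop-out adjustment appears anywhere in the section.

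**The concern.** The words after i.e. should restate what comes before them. In the Study 1A sentence they replace 22 with 18, which is the requirement from the bullet above with no allowance for loss. On its face the sentence allows a total of 66 (3 × 22) or 54 (3 × 18).

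The drop-out step also does not work out exactly. Dividing 18 by the proportion expected to remain gives slightly more than 22, and the same 22 is reused in the other three studies.

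A recruitment target tells the team when to stop enrolling, and readers later compare achieved enrolment with it. It should be one number, and it should agree with the drop-out rate printed beside it.

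**Working it through.** **Inputs, all from section 3.7.** Required number: 18 per group, 3 × 18 = 54 in total. Drop-out: 20%. Recruitment: 22 per group. Means: 7.0 (PlayMed) and 6.0 (control), SD 1.4. Type I error 0.05, power 0.8. Sidedness is not stated. I assume two-sided and give the one-sided result as the other end of the range.

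**1. The two targets, side by side.**

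| Study | Per group, first statement | Per group, after i.e. |
|---|---|---|
| 1A | 22 | 18 / 18 / 18 |
| 2A | 22 | 22 / 22 / 22 |
| 1B and 2B | 22 | 22 / 22 / 22 |

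Only the Study 1A line disagrees with itself.

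**2. Where 22 could come from.** Multiplying gives 18 × 1.2 = 21.6, which rounds up to 22. Dividing gives 18/0.8 = 22.5, which becomes 22 if rounded down. The plan shows no formula, so either route is an inference.

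**3. The drop-out step.** The number to recruit is n/(1 − drop-out).

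- Needed to keep 18: 18/(1 − 0.20) = 22.5, so 23 per group, or 3 × 23 = 69 with equal groups.
- Expected completers from 22: 22 × 0.8 = 17.6, which is 0.4 below 18.
- Loss that 22 can absorb: 1 − 18/22 = 18.2%.

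**4. What the shortfall costs.** For PlayMed against control, the standardised difference is 1.0/1.4 = 0.714. Two-sided 5% t-test power is 54.9% at 18 per group and 53.9% at 17.6, a difference of about 1 point.

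**5. Does 18 give 80%?** The normal approximation gives n = 2 × (1.96 + 0.84)²/0.714², which is about 30.8, so 31 per group. The t-test needs 31.8, so 32. At 18 per group, power is about 55% by t-test and 57% by normal approximation. If the test were one-sided at 5%, 25 per group would be needed, and 18 would give about 68%. With the SD at 1.4, none of these variants reproduces 18 per group at 80% power.

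**The case against.** The strongest reply is that nobody would be misled. The bullet before the disputed sentence defines 18 as the number required by the power calculation. The sentence itself says 22 will be recruited, and the lines for the other studies say 22 throughout. The stray 18s are either carried over or meant as the number left after drop-out (17.6, rounded). This largely stands: 22 is the evident target. The sentence still does not say so, and it needs correcting.

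It can also be said that 22 against 23 is a matter of rounding. That stands too. One person per group, 0.4 of an expected completer and about 1 point of power are not a material loss.

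Two stronger readings are tempting, and the documents support neither.

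- A reader might infer that Study 1A will enrol only 18 per group, leaving 18 × 0.8 = 14.4 completers and about 46% power. That requires taking the second half of the sentence over the first half and over the lines for the other three studies. Nowhere else does the plan use 18 as a recruitment number.
- A reader might judge 22 by the chance that all three groups keep at least 18, which is low (about 16% with independent 20% loss). The plan sets no such criterion, and 23 per group would meet it only about 34% of the time.

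Finally, section 4.3 (Missing Data) imputes the group mean for people who do not attend, so the analysed number would nominally be 22. Imputed means add no information, so completers remain the count that matters for power.

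**Conclusion.** The Study 1A sentence is wrong as written because it gives two recruitment numbers. The error is one of wording, and the intended number is clear from the other studies.

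The drop-out allowance is slightly short in all four studies: 22 covers 18.2% rather than 20%. The size is one recruit and 0.4 expected completers per group, and about 1 point of power for PlayMed against control. That power figure assumes a two-sided 5% t-test and the pilot means and SD.

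A reader might also infer that keeping 18 completers, by recruiting 23, would protect the stated 80% power. It would not. From the plan's own inputs, 18 completers give about 55% under the two-sided assumption (about 68% if one-sided), and 80% needs about 32 completers per group (25 if one-sided). That is a larger and separate problem with the base figure, and correcting the recruitment sentence leaves it untouched.

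**What to change.** In the Study 1A sentence, change each of the three group figures after i.e. from 18 to 22 and add the total of 66. This part applies to Study 1A only, since the other lines are consistent.

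For all four studies, show the drop-out formula and choose one of two statements:

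- keep 22 per group, and say that it allows for about 18% drop-out and leaves 17.6 expected completers per group at 20%; or
- keep 18 completers as the target at 20% drop-out, and print 23 per group, 69 in total.

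As a separate correction, re-derive the base figure of 18, naming the hypothesis tested and whether the test is one- or two-sided, or restate the power that 18 gives.

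Cost: the first option changes wording only and makes the stated drop-out allowance slightly smaller. The second adds 69 − 66 = 3 participants per study. The separate correction costs more. Any restated power would be substantially below 0.8, at about 54% to 55% for PlayMed against control under the two-sided assumption. Holding 80% would mean a clearly larger study: 32/0.8 = 40 recruits per group for that comparison alone.
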